12. ASSESSMENT OF SAFETY

12.1 Adverse Events

12.1.1 Definitions

An AE is defined as any untoward medical occurrence in a subject administered an IP that does not necessarily have a causal relationship with the treatment. An AE can therefore be any unfavorable and unintended sign (eg, an abnormal laboratory finding), symptom (eg, rash, pain, discomfort, fever, dizziness, etc.), intercurrent disease (eg,

peritonitis, bacteremia, etc.), or outcome of death temporally associated with the use of an IP, whether or not considered causally related to the IP.

Each Grade 3 or Grade 4 abnormal laboratory value will be reported as an AE, unless the abnormal value relates to a diagnosis that is itself recorded as an AE or has no clinical correlate.

Events relating to clinical deterioration due to disease progression as a result of the underlying malignancy are not to be considered or analyzed as AEs (or SAEs), but will be recorded on the CRF.

A TEAE is defined as any event not present prior to the initiation of the treatments or any event already present that worsens in either intensity or frequency following exposure to the treatments.

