12.1.1.1 Serious Adverse Event

A **serious** adverse event (SAE) is defined as an untoward medical occurrence that at any dose meets one or more of the following criteria:

- Outcome is fatal/results in death (including fetal death)
- Is life-threatening – defined as an event in which the subject was, in the judgment of the investigator, at risk of death at the time of the event; it does not refer to an event that hypothetically might have caused death had it been more severe
- Requires inpatient hospitalization or results in prolongation of an existing hospitalization – inpatient hospitalization refers to any inpatient admission, regardless of length of stay
- Results in persistent or significant disability/incapacity (ie, a substantial disruption of a person's ability to conduct normal life functions)
- Is a congenital anomaly/birth defect
- Is a medically important event – a medical event that may not be immediately life-threatening or result in death or require hospitalization but may jeopardize the subject or may require medical or surgical intervention to prevent one of the other outcomes listed in the definitions above

Examples of such events are:

- Intensive treatment in an emergency room or at home for allergic bronchospasm, blood dyscrasias, or convulsions that do not result in hospitalization, or development of drug dependence or drug abuse
- Reviewed and confirmed seroconversion for HIV, hepatitis A virus (HAV), HBV, HCV, hepatitis E virus (HEV), or parvovirus B19 (B19V)
- Uncomplicated pregnancies, following maternal or paternal exposure to IP are not considered an (S)AE; however, any pregnancy complication or pregnancy termination by therapeutic, elective, or spontaneous abortion shall be considered an SAE

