12.1.2 Assessment of Adverse Events

For the purposes of this study, each non-serious untoward medical occurrence experienced by a subject undergoing study-related procedure(s) before first exposure to IP will be recorded on the AE CRF; however, these events will not be considered as AEs and will not be included in the analysis of AEs.

Each TEAE (non-serious AE or SAE) from the first IP exposure until study completion/discontinuation or 30 days (± 7 days) following the last IP treatment will be described on the AE CRF using the medical diagnosis (preferred), or, if no diagnosis could be established at the time of reporting the AE, a symptom or sign, in standard medical terminology in order to avoid the use of vague, ambiguous, or colloquial expressions (see definition in Section 12.1). Each AE will be evaluated by the investigator for:

- Seriousness as defined in Section 12.1.1.1
- Severity as defined in Section 12.1.2.1
- Causal relationship to IP exposure or study procedure as defined in Section 12.1.2.2.

For each AE, the outcome (ie, recovering/resolving, recovered/resolved, recovered/resolved with sequelae, not recovered/not resolved, fatal, unknown) and if applicable action taken (ie, dose increased, dose not changed, dose reduced, drug interrupted, drug withdrawn, not applicable, or unknown) will also be recorded on the AE CRF. Recovering/resolving AEs will be followed until resolution, medically stabilized, or 30 days after the last IP administration, whichever comes first. If the severity rating for an ongoing AE changes before the event resolves, the original AE report will be revised (ie, the event will not be reported as separate AE). During the course of any AE, the highest severity rating will be reported.

Deviations from the protocol-specified dosage (including overdosing [any dose that is at least 20% higher than the highest explored dose level], underdosing [any dose that is lower than the intended explored dose level by 10%], abuse, and withdrawal [see

Section 9.3]), treatment errors (including incorrect route of administration, use of an incorrect product, and deviations from the protocol-defined dosing schedule), failures of expected pharmacological actions, and unexpected therapeutic or clinical benefits will be followed with regard to occurrence of AEs, lack of efficacy, and/or other observations because these events may be reportable to regulatory authorities.

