12.1.2.3 Safety Reporting

Adverse events/SAEs will be assessed at all study visits as outlined in the Schedules of Study Procedures and Assessments (see [Table 3](#), [Table 4](#), and [Table 5](#)) and Section [12.1.2](#).

Adverse events/SAEs are to be recorded on the AE page of the eCRF. Each event should be recorded separately.

Any SAE, including death due to any cause, which occurs during this study, whether or not related to the investigational product, must be reported immediately (within 24 hours of the study center's first knowledge of the event). All SAEs must be reported via the Electronic Data Capture (EDC) system by completing the relevant eCRF page(s) in English. Once the SAE has been recorded in the EDC system, the sponsor and other designated recipients will be informed of the event automatically. For instances in which the EDC may become unavailable, SAEs must be reported using the back-up paper SAER Form to meet the 24 hour timeline requirement (for contacts and instructions refer to the SAER Form). Once the EDC becomes available, the site must enter all SAE data as reported on the back-up paper SAER Form on the applicable eCRF pages.

The reported event will contain as much available information concerning the SAE to enable the sponsor or designee to file a report, which satisfies regulatory reporting requirements. The initial SAE information reported on the applicable eCRF pages (or back-up SAER Form, if applicable) must at least include the following:

- Protocol Number
- Subject identification number and demographics (gender, age at onset of event and/or date of birth)
- Investigational product exposure
- Medical Term for Event (Diagnosis preferably)
- Description of the (S)AE, including:
 - Date of onset
 - (S)AE treatment (drug, dose, route of administration)
 - Causal relationship by the Investigator
 - Measures taken (ie, action taken regarding investigational product in direct relationship to the AE)
 - Outcome
- Seriousness criteria (ie, death, life-threatening, or other criterion)

- Cause of death
- Autopsy findings (if available)
- Name, address, fax number, email, and telephone number of the reporting Investigator (for paper SAER Forms)

The serious adverse event reporting contact information is provided below by country:

Country	Telephone	Fax
Germany	PPD	PPD
Spain	PPD	PPD
United Kingdom	PPD	PPD
United States	PPD	PPD

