The adverse events summaries listed in [Table 3](#) will be provided for study cohort, integrated treatment group, and totals for the table for the safety analysis set:

Table 3: AE tables produced for treatment with and without stratification

AE Summary	Study Cohort	Integrated Treatment Group

AE Summary	Study Cohort	Integrated Treatment Group
TEAEs summary	Y	Y
TEAEs by System Organ Class and Preferred Term	Y	Y
TEAEs by Preferred Term and by Descending Incidence	Y	N
TEAEs by System Organ Class and Preferred Term and CTCAE Grade	Y	N
Grade 3 or Higher TEAEs by System Organ Class and Preferred Term	Y	N
Serious TEAEs by System Organ Class and Preferred Term	Y	Y
Non-Serious TEAEs by System Organ Class and Preferred Term and by Descending Incidence	Y	N
Serious TEAEs by System Organ Class and Preferred Term and CTCAE Grade	Y	N
Treatment-Related TEAEs by System Organ Class and Preferred Term	Y	N
Treatment-Related TEAEs by Preferred Term and by Descending Incidence	Y	Y
Treatment-Related TEAEs by System Organ Class and Preferred Term and CTCAE Grade	Y	N
TEAEs Leading To Study Drug Discontinuation by System Organ Class and Preferred Term	Y	Y
TEAEs Leading To Study Drug Discontinuation by System Organ Class and Preferred Term and CTCAE Grade	Y	N
TEAEs Leading to Death by System Organ Class and Preferred Term	Y	Y

Listings of all AEs and also all serious AEs will be produced.

A Listing will be produced for AEs with genetic information, actual drug received, and cycles on treatment.

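### Protocol 12.1.1 keeps progression deterioration out of the AE/SAE analysis, 12.1.2.3 makes death from any cause a reportable SAE, and no planned safety table of deaths is independent of that choice

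*Protocol*

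**What the plan says.** Protocol 12.1.1 states that events of clinical deterioration "due to disease progression as a result of the underlying malignancy are not to be considered or analyzed as AEs (or SAEs"). The section adds that these events still go on the CRF, without naming the form. The AE definition in the same section includes the "outcome of death temporally associated with the use of an IP, whether or not considered causally related to the IP".

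Protocol 12.1.1.1 lists as an SAE criterion "Outcome is fatal/results in death (including fetal death"), without exempting deaths from progression. Protocol 12.1.2.3 requires reporting within 24 hours of "Any SAE, including death due to any cause, which occurs during this study, whether or not related to the investigational product". It sends AEs and SAEs to the AE page of the eCRF and names cause of death among the items of the SAE report. Protocol 12.1.2 sets the collection window: "from the first IP exposure until study completion/discontinuation or 30 days (± 7 days) following the last IP treatment".

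SAP 8.3 defines a TEAE as an event that is new or worsened after treatment starts. It does not mention progression. Its Table 3 plans "TEAEs Leading to Death by System Organ Class and Preferred Term" along with several serious-TEAE tables, plus listings of AEs and serious AEs. It plans no table of all deaths. All-cause death is analyzed as OS from randomization (SAP 7.2.1.1), in the efficacy population (SAP 4.1). The trial is open-label (Protocol 8.5, SAP 2.5).

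**The concern.** Take a third- or fourth-line subject who deteriorates and dies two weeks after the last dose, and whose death the investigator puts down to the cancer. A site that works from 12.1.1 may record the deterioration on the CRF and file no SAE. A site that works from 12.1.2.3 files an SAE with a fatal outcome on the AE page. Both can say they followed the protocol.

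The consequence lies in the safety tables. In the first case the death does not enter the fatal or serious TEAE counts. In the second it does, unless someone removes it later, and the SAP gives no instruction to do so. Safety and tolerability is a secondary objective, and the arms are small enough for a few deaths to change the rates visibly. The investigator who attributes the death knows the treatment, and no planned safety output counts deaths without using that attribution.

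**Working it through.** The plan states no figure on this point, so there is none to reproduce. The check compares the sections and then works out what one death is worth.

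**Step 1: a progression-attributed death inside the AE window, section by section.**

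| Source | Treatment of that death |
|---|---|
| Protocol 12.1.1, exclusion | The deterioration is neither considered nor analyzed as an AE or SAE; CRF record only |
| Protocol 12.1.1, AE definition | Death close in time to IP can be an AE, whatever its cause |
| Protocol 12.1.1.1 | Fatal outcome is an SAE criterion; no exception |
| Protocol 12.1.2.3 | Reported within 24 hours; any cause; no exception |
| Protocol 10.5 | Death is given as an example of an AE when reasons for discontinuation are listed |
| SAP 8.3 | Any new or worsened event is a TEAE; no progression filter |

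None of these says which rule takes precedence.

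**Step 2: the same comparison for a non-fatal progression event, such as an admission for deterioration.** The exclusion in 12.1.1 applies, and 12.1.2.3 makes no special statement about it. The attribution is still a matter of opinion, but the sections do not contradict each other. The contradiction is confined to deaths.

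**Step 3: value of one reclassified death.** The planned Part 2 sizes are 44 in Arm A and 22 in Arm B (Protocol 13.1). I assume that all are treated and so belong to the Safety Analysis Set.

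- Arm A: 1/44 = 0.0227, or 2.3 percentage points.
- Arm B: 1/22 = 0.0455, or 4.5 percentage points.

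**Step 4: how this scales.** The documents give no rate of progression-attributed deaths in the window. Purely as an assumption, take 5% to 20% in both arms:

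- Arm A: 0.05 × 44 = 2.2 to 0.20 × 44 = 8.8, so about 2 to 9 deaths (2/44 = 4.5% to 9/44 = 20.5%).
- Arm B: 0.05 × 22 = 1.1 to 0.20 × 22 = 4.4, so about 1 to 4 deaths (1/22 = 4.5% to 4/22 = 18.2%).

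If every site switched from one reading to the other, both rates would move together. The difference between arms would change by 4.5 − 4.5 = 0 points at the low end and 20.5 − 18.2 = 2.3 points at the high end. Only if one arm counted every such death and the other none would the spurious difference (A minus B) reach ±4.5 points at 5%, or +20.5 to −18.2 points at 20%. Those are extreme bounds on an assumed rate, not expected values.

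**Step 5: endpoints that do not depend on the classification.** OS counts death from any cause. PFS counts death from any cause, subject to its censoring rules. Neither uses AE status.

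**The case against.** The best reply is that the sections do different jobs. Section 12.1.2.3 governs rapid reporting; 12.1.1 governs analysis and makes no distinction by arm. A death can be reported within 24 hours and then left out of the AE tables. SAP 5.5 lists only two departures from the protocol's planned analysis, the dropped interim analysis and the PFS start date, so the exclusion still stands. On this view the SAP need not repeat it.

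Much of this stands: 12.1.1 is an analysis rule as well as a reporting rule. It does not close the gap, because 12.1.1 also governs whether the event is considered an SAE at all, which is what 12.1.2.3 decides the other way for deaths. The SAP also gives no step for removing a reported progression death from tables whose TEAE definition would include it.

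A reader might go further than the documents allow in four ways:

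- *That all serious-event rates are caught in the contradiction.* Step 2 shows that non-fatal progression events are not.
- *That a toxic death misattributed to progression would vanish from every safety summary.* The exclusion covers only deterioration due to the malignancy. A toxicity recorded before death remains an AE, and OS counts deaths by arm. The Full Analysis Set keeps treated subjects who die within 18 weeks even without a scan.
- *That the DSMB's review is compromised.* Its activities are set out in a charter that is not among these documents.
- *That the between-arm bias is 5 to 20 points.* That range is an assumed death rate, and the shift it describes is between two uniform readings. Nothing in the documents suggests that sites would split by arm.

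OS does not replace a safety table of deaths. It runs from randomization, is not limited to the period around dosing, does not give cause, and uses the efficacy population.

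**Conclusion.** The point holds for deaths. Two protocol sections lead to different classifications of a progression-attributed death within the AE window, and the SAP neither settles which applies nor plans a safety output that is independent of the choice. The size is 2.3 points per death in Arm A and 4.5 in Arm B, given the planned 44 and 22 subjects. The total cannot be stated because the documents give no rate for such deaths. The point concerns how fatal and serious TEAE counts can be interpreted; the primary comparison and OS do not change. It should be fixed before the tables are produced, because otherwise a reader of the fatal-TEAE table cannot tell which deaths it contains.

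**What to change.** 1. Reconcile Protocol 12.1.1 and 12.1.2.3 so that one rule governs how deaths attributed to progression are reported and classified.
2. Carry that rule into SAP 8.3, stating whether such deaths are in or out of the fatal and serious TEAE tables, identically for both arms.
3. Add one table of all deaths by arm in the Safety Analysis Set, split into deaths on treatment or within 30 days of the last dose and later deaths. The all-cause total should be the main figure, since it needs no attribution. Investigator-attributed cause (progression, AE, other) is a secondary breakdown, because it carries the same open-label attribution.
4. Confirm that date and cause of death are captured on the CRF for every death. Cause of death is named only among the SAE report items in 12.1.2.3, so a site that files no SAE may not record it.

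The cost is a protocol clarification, a sentence in the SAP, one extra table and possibly one CRF field. Reported fatal-event counts may look higher. Treatment, sample size and the primary analysis are untouched.

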12.1.1.1 Serious Adverse Event

A **serious** adverse event (SAE) is defined as an untoward medical occurrence that at any dose meets one or more of the following criteria:

- Outcome is fatal/results in death (including fetal death)
- Is life-threatening – defined as an event in which the subject was, in the judgment of the investigator, at risk of death at the time of the event; it does not refer to an event that hypothetically might have caused death had it been more severe
- Requires inpatient hospitalization or results in prolongation of an existing hospitalization – inpatient hospitalization refers to any inpatient admission, regardless of length of stay
- Results in persistent or significant disability/incapacity (ie, a substantial disruption of a person's ability to conduct normal life functions)
- Is a congenital anomaly/birth defect
- Is a medically important event – a medical event that may not be immediately life-threatening or result in death or require hospitalization but may jeopardize the subject or may require medical or surgical intervention to prevent one of the other outcomes listed in the definitions above

Examples of such events are:

- Intensive treatment in an emergency room or at home for allergic bronchospasm, blood dyscrasias, or convulsions that do not result in hospitalization, or development of drug dependence or drug abuse
- Reviewed and confirmed seroconversion for HIV, hepatitis A virus (HAV), HBV, HCV, hepatitis E virus (HEV), or parvovirus B19 (B19V)
- Uncomplicated pregnancies, following maternal or paternal exposure to IP are not considered an (S)AE; however, any pregnancy complication or pregnancy termination by therapeutic, elective, or spontaneous abortion shall be considered an SAE

12.1.1.2 Suspected Unexpected Serious Adverse Reaction (SUSAR)

Any suspected adverse reaction to study treatment (ie, including active comparators) that is both serious and unexpected.

The event(s) must meet all of the following

- Suspected adverse reaction
- Serious
- Unexpected
- Assessed as related to study treatment

Once determined to meet the criteria for a SUSAR, an SAE should be submitted to regulatory agencies expeditiously.

12.1.1.3 Non-Serious Adverse Event

A **non-serious** AE is an AE that does not meet the criteria of an SAE.

12.1.1.4 Unexpected Adverse Events

An unexpected adverse event is an AE whose nature, severity, specificity, or outcome is not consistent with the term, representation, or description used in the Reference Safety Information (RSI) (eg, IB, package insert). The expectedness of AEs will be determined by the sponsor using the IB as the RSI. This determination will include considerations such as the number of AEs previously observed, but not on the basis of what might be anticipated from the pharmacological properties of a medicinal product.

For the purposes of this study, all AEs experienced by a subject, including unexpected AEs, will be recorded on the AE CRF.

12.1.1.5 Preexisting Diseases

Preexisting diseases that are present before entry in to the study are described in the medical history, and those that manifest with the same severity, frequency, or duration after IP exposure, will not be recorded as AEs. However, when there is an increase in the severity, duration, or frequency of a preexisting disease, the event must be described on the AE CRF.

12.1.2 Assessment of Adverse Events

For the purposes of this study, each non-serious untoward medical occurrence experienced by a subject undergoing study-related procedure(s) before first exposure to IP will be recorded on the AE CRF; however, these events will not be considered as AEs and will not be included in the analysis of AEs.

Each TEAE (non-serious AE or SAE) from the first IP exposure until study completion/discontinuation or 30 days (± 7 days) following the last IP treatment will be described on the AE CRF using the medical diagnosis (preferred), or, if no diagnosis could be established at the time of reporting the AE, a symptom or sign, in standard medical terminology in order to avoid the use of vague, ambiguous, or colloquial expressions (see definition in Section 12.1). Each AE will be evaluated by the investigator for:

- Seriousness as defined in Section 12.1.1.1
- Severity as defined in Section 12.1.2.1
- Causal relationship to IP exposure or study procedure as defined in Section 12.1.2.2.

For each AE, the outcome (ie, recovering/resolving, recovered/resolved, recovered/resolved with sequelae, not recovered/not resolved, fatal, unknown) and if applicable action taken (ie, dose increased, dose not changed, dose reduced, drug interrupted, drug withdrawn, not applicable, or unknown) will also be recorded on the AE CRF. Recovering/resolving AEs will be followed until resolution, medically stabilized, or 30 days after the last IP administration, whichever comes first. If the severity rating for an ongoing AE changes before the event resolves, the original AE report will be revised (ie, the event will not be reported as separate AE). During the course of any AE, the highest severity rating will be reported.

Deviations from the protocol-specified dosage (including overdosing [any dose that is at least 20% higher than the highest explored dose level], underdosing [any dose that is lower than the intended explored dose level by 10%], abuse, and withdrawal [see

Section 9.3]), treatment errors (including incorrect route of administration, use of an incorrect product, and deviations from the protocol-defined dosing schedule), failures of expected pharmacological actions, and unexpected therapeutic or clinical benefits will be followed with regard to occurrence of AEs, lack of efficacy, and/or other observations because these events may be reportable to regulatory authorities.

Any pregnancy of the subject or partner that is confirmed within 90 days after administration of imalumab will be reported on a Pregnancy Form and followed up at estimated date of delivery and 1 year postdelivery, if feasible.

If an investigator becomes aware of an SAE occurring in a subject after study completion, the SAE must be reported on the provided Serious Adverse Event Report (SAER) Form within 24 hours after awareness; no additional reporting on CRFs is necessary.

